11.3.7 Adverse events

All analyses of AEs will be based on the number of subjects with AEs (and not on the number of AEs) except otherwise specified and using the safety set.

Adverse event will be coded with the MedDRA dictionary.

The time period for the assessment of AEs will be divided into 5 mutually exclusive and exhaustive periods (see Table 3 below):

	Start	End
Before IMP/AMP	Informed consent signature	Start of the first administration
Period 1	Start of the first administration	Start of the second administration
Period 2	Start of the second administration	Start of the third administration
Period 3	Start of the third administration	Start of the fourth administration
Period 4	Start of the fourth administration	Day 12 (except pregnancy cf.9.39.3)

Table 3: Time periods for the assessment of AEs

Events will be classified by trial products according to time of onset in the corresponding cycle related to trial products.

Events will be classified as treatment-emergent if they have started since the first administration.

Partial start dates/times will be queried. If information is not available to reliably allocate to a session and period, the allocation will be agreed at the data review meeting before database lock. If there is any doubt about treatment emergence, AEs will be classified as treatment emergent.

Overall overview

The number (%) of subjects having at least one AE (AE) as follows will be summarized for each trial product and overall for:

- At least one TEAE
- At least one AE with each of the following classification of intensity

- Mild
- Moderate
- Severe
- At least one adverse reaction (relationship to trial treatment classified as ‘Related’)
- At least one AE with each of the following classifications of action taken with trial treatment:
 - Dose not changed
 - Trial product withdrawn
- At least one AE with each of the following classifications of outcome:
 - Recovered/resolved
 - Recovered/resolved with sequelae
 - Not recovered/Not resolved
 - Fatal

The table will show the same information for serious AE, defined as AEs with serious classified as ‘yes’ or missing.

The table will be repeated for all TEAEs.

Distribution of AEs and SAEs

A table will be presented showing the total numbers of AEs and SAEs and the distribution of AEs (number [%] of subjects with 0, 1, 2 etc. AEs) for each IMP/AMP and overall. The table will also show the same information for SAEs defined as TEAEs with serious classified as ‘yes’ or missing, unless the number of SAEs make this uninformative.

Summaries by System Organ Classes (SOC) and Preferred Term (PT)

Summaries by SOC and PT will be presented for all treatment-emergent events and all related treatment-emergent events for each IMP/AMP and overall.

 CONFIDENTIAL	Protocol No. GDX-44-006 Version No. 5.0 including amendment 03 Date 31 August 2018	Page 68 / 80
---------------------------------------------------------------------------------------------------	------------------------------------------------------------------------------------------	--------------

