9.1.2 Collection and Recording of Adverse Events

The Investigator or his/her designee will invite the subject to report any experienced abnormality as part of the usual clinical follow-up. In addition, any biological value assessed as significant by the Investigator should be considered as AE.

In order to ensure complete safety data collection, all Adverse Events occurring from the screening visit (ICF signature) until the end of the confinement period, must be reported and followed even if no IMP or moxifloxacin were administered. Only related Adverse Events (serious or not) or AESI (related or not) will be recorded during follow-up visits.

AE should be reported and documented in the medical file and the appropriate section of the CRF

As reminder the subject's participation is defined as the period from the screening visit (ICF signature) to the last trial visit in the general case and defined in [section 10](#) in case of premature discontinuation.

Reported AE is followed up from onset to recovery or stabilization of sequelae. If no follow-up is performed, the investigator must provide a justification in the medical file.

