9.1.3 Description of Adverse Events

The following guidelines and definitions should be used by the investigator for the description of an AE when reporting information in CRF and any specific AE report forms:

- **Nature of AE:** preferably an overall diagnosis or syndrome, rather than individual symptoms or signs. The investigator must report AE using standard medical terminology. The same terms should be used in the source documentation and in the CRF.
- **Date and time of onset:** date and clock time of the AE start
- **Intensity:**

- Mild: the subject is aware of the sign or symptom, but it does not interfere with her/his usual daily activities and/or it is of no clinical consequence
- Moderate: the AE interferes with the usual daily activities of the subject or it is of some clinical consequence
- Severe: the subject is unable to work normally or to carry out his/her usual daily activities, and/or AE is of definite clinical consequence.
- **Date of the event end** (or consolidation): The real date of event end will be entered if the event has come to its end. If the AE is still ongoing by the time of end of trial follow-up for the subject (i.e. last trial visit), the subject should be followed-up until AE resolution or a justification should be provided by the Investigator (i.e. chronic disease) in the medical file.
- **Causal relationship to the Investigational Medicinal Product or moxifloxacin:**
 - Related: the definition of adverse reaction implies a reasonable possibility of a causal relationship between the event and the IMP or moxifloxacin. This means that there are facts (evidence) or arguments to suggest a causal relationship.
 - Not related: Applicable when no IMP or moxifloxacin have been administered (pre-administration period) or when no causal relationship exists between the trial drug and the event, but an obvious alternative cause exists (e.g. the subject's underlying medical condition or concomitant therapy).
- **Causal relationship to a trial procedure:**
 - Related
 - Not related
- **Outcome:**
 - Recovered/Resolved: the AE is no longer present at any intensity or return to baseline values for biological data.
 - Recovered/Resolved with sequelae: the AE is resolved but residual effects are still present.
 - Not recovered/Not Resolved: the AE is still present at the last contact with the subject.
 - Fatal: this AE caused or directly contributed to subject's death.

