The table will show the same information for serious AE, defined as AEs with serious classified as ‘yes’ or missing. The table will be repeated for all TEAEs.

A table will be presented showing the total numbers of AEs and SAEs and the distribution of AEs (number [%] of subjects with number of AEs) for each IMP/AMP and overall. The table will also show the same information for SAEs defined as TEAEs with serious classified as ‘yes’ or missing, unless the number of SAEs make this uninformative.

Summaries by SOC and PT will be presented for all treatment-emergent events and all related treatment-emergent events for each IMP/AMP and overall.

Adverse events during follow-up period will be presented overall by SOC and PT.

Data listings will present all AEs reported, including non-TEAEs. Adverse event listings will be sorted by subject number and will display also the study procedure, body system, and preferred term, time of onset, duration, intensity, seriousness, outcome, relationship to the IMP/AMP, relationship to a study procedure, action taken with IMP/AMP, IMP unblinding, AE-targeted medication, other AE-targeted action, date and time of IMP/AMP administration (presented in CSR appendix 16.2.7).

AE Duration will be computed in days as Date of End of AE - Date of Onset of AE + 1. Date and time of administration displayed will be those of trial product administration preceding the date and time of onset of the AE. If the AE started before Day 1 or after the follow-up period, no date and time of administration will be displayed.

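### Treatment emergence and product allocation of AEs rest on onset alone, with no provision for an event that worsens after dosing

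*Protocol*

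**What the plan says.** **Emergence.** Protocol 11.3.7: "Events will be classified as treatment-emergent if they have started since the first administration". SAP 5.6.2 repeats the sentence.

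**Product.** Protocol 11.3.7: "Events will be classified by trial products according to time of onset in the corresponding cycle related to trial products". The SAP 5.6.2 listings follow the same logic: "Date and time of administration displayed will be those of trial product administration preceding the date and time of onset of the AE".

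**Recording.** Protocol 9.1.2 requires that "all Adverse Events occurring from the screening visit (ICF signature) until the end of the confinement period, must be reported and followed", and adds: "Reported AE is followed up from onset to recovery or stabilization of sequelae". For the start of an event, protocol 9.1.3 asks for the "date and clock time of the AE start". It also asks for an intensity of mild, moderate or severe, without saying whether this is the grade at onset, the last grade or the worst. Neither section says whether a change of grade opens a new record.

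**Outputs.** Protocol 11.3.7, and SAP 5.6.2 in the same terms: "Summaries by SOC and PT will be presented for all treatment-emergent events and all related treatment-emergent events for each IMP/AMP and overall". The overview table, which includes the intensity rows, is made for all AEs and then repeated for TEAEs. SAP 5.6.2 lists every AE, including those that are not treatment-emergent.

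**Doubtful cases.** After the text on partial dates, protocol 11.3.7 adds: "If there is any doubt about treatment emergence, AEs will be classified as treatment emergent".

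**The concern.** An event already present at dosing that gets worse afterwards is a possible product effect. The written rules have no place for it, because they look only at when the event began.

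The situation is foreseeable here. AEs are collected from consent, which may be up to 28 days before inclusion. Four 72-hour periods then run back to back, so an event from one period can easily be ongoing at the next administration. The action-taken categories in protocol 9.1.3 themselves allow for a product being given unchanged while an AE is present.

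At stake is the by-product clinical safety comparison of the two P03277 doses, placebo and moxifloxacin, which serves a secondary objective. Where AE counts are low, one severe or related event in the wrong column, or in none, is noticeable.

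The SAP does handle worsening elsewhere. Section 2.2.2 counts ECG morphology changes that are either new or worse than baseline. The AE sections have no counterpart.

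**Working it through.** The plan gives no figure on this point to reproduce. The check is how the written rules treat each case, and then how far a table cell can move.

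**1. Cases under the rules as written**

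| Event | TEAE? | SOC/PT tables | Product |
|---|---|---|---|
| Starts after consent and before the first administration, worsens after dosing | No | Absent | None by onset; kept in the all-AE overview (overall) and listings |
| Starts in Period 1, worsens after the Period 2 product | Yes | Present | Period 1 product only |
| Starts in a period, does not worsen | Yes | Present | That period's product |

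So non-emergence arises only for onset before the first administration. Between later periods the issue is allocation.

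**2. Largest movement per affected subject**

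Inputs: 48 randomized subjects, all assumed to receive every product; tables count subjects with at least one AE (protocol 11.3.7).

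- Any-TEAE row: if the worsening were a new AE, the existing AE would stay with the earlier product and the later product would gain one subject. Movement = 1/48 = 2.1 percentage points, provided the subject has no other TEAE under the later product.
- Intensity row such as severe, if the worst grade is what is recorded: the subject leaves the earlier product's row and enters the later product's row. Change in the difference = 2/48 = 4.2 points.
- Intensity row, if the grade at onset is recorded: the earlier product's row does not change and the later product gains 1/48 = 2.1 points.

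**3. Where a worsening lands by product order**

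In the example sequences of protocol 3.1, each of the 12 ordered pairs of adjacent products occurs once, in 12 subjects, and each product comes first in 12 of 48. A worsening after a given product therefore follows the pre-dose interval in 12/48 = 1/4 of subjects and each of the other three products in 1/4. Under the onset rule it is never placed with the product just given.

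**4. Illustration with assumed rates**

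The documents give no AE rates. Assume that a share q of subjects enter each period with an AE ongoing from the interval just before. Assume that it worsens with probability 0.5 after 0.3 mmol/kg and 0.1 after any other product, and that the worst grade is recorded. For q = 5%:

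- Arising after 0.3 mmol/kg: 48 × 0.05 × 0.5 = 1.20 subjects.
- Charged to 0.3 mmol/kg: 3 × 12 × 0.05 × 0.1 = 0.18.
- Arising after placebo: 48 × 0.05 × 0.1 = 0.24.
- Charged to placebo: 12 × 0.05 × (0.5 + 0.1 + 0.1) = 0.42.
- Not treatment-emergent: 12 × 0.05 × (0.5 + 0.1 + 0.1 + 0.1) = 0.48.

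| q | 0.3 mmol/kg: arising / charged | Placebo: arising / charged | Not emergent |
|---|---|---|---|
| 2% | 0.48 / 0.07 | 0.10 / 0.17 | 0.19 |
| 5% | 1.20 / 0.18 | 0.24 / 0.42 | 0.48 |
| 10% | 2.40 / 0.36 | 0.48 / 0.84 | 0.96 |

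Even with a strong assumed effect, few subjects are involved. If every product worsened events equally often, the balanced order would cancel the misplacement between products on average.

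**The case against.** The best defence is that the documents do not forbid a second record. Protocol 9.1.1 defines an AE broadly enough for a post-dose worsening to qualify, and CRF completion instructions, which are not among the documents, may already require a new entry. If so, the onset rule would allocate it correctly and most of the problem would disappear. This stands as a limit on certainty. It does not remove the gap, because neither document says so and the result depends on that choice.

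Second, doubtful cases count as treatment-emergent. That helps little: a known start before the first administration leaves no doubt, and the rule does not choose between products.

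Third, a later worsening may be natural progression of the earlier event, so onset allocation is not always wrong. That is fair, but it does not justify hiding the timing of the worsening from the by-product tables.

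Fourth, the consequence is small. Subjects with acute illness are excluded. Laboratory values, vital signs and safety ECGs are compared with baseline in their own analyses, and injection-site tolerance is assessed after each injection. This stands.

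A reader might also go further than the text allows:

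- **Any event that worsens after a dose is not a TEAE.** Emergence is judged against the first administration only.
- **The worst grade is charged to the earlier product.** The recorded grade is not specified.
- **A worsened pre-dose event is lost altogether.** It stays in the all-AE overview and the listings.
- **The tables are biased against finding a P03277 effect.** Events that start on P03277 and worsen on a control stay with P03277. A net direction needs an assumption about which product worsens events more.

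**Conclusion.** The concern holds as a gap in the definitions. Both documents decide emergence and product by onset alone, and followed literally they give the wrong result in two foreseeable cases. A worsened AE with onset before the first administration is left out of the TEAE and SOC/PT tables, and a worsening in a later period is not shown under the product given just before it.

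The movements of 2.1 and 4.2 points per affected subject are ceilings. They rest on 48 subjects per product and no other qualifying AE under the later product; the larger one also needs the worst grade to be the recorded grade. How many subjects would be affected cannot be derived from the documents; under the assumed rates above, 0.48 to 2.40 subjects have a worsening after 0.3 mmol/kg. The direction depends on the order of products. These tables are descriptive and secondary, and nothing here touches the QTcF analysis. The point merits a short correction and does not support a claim that the safety comparison is unreliable.

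**What to change.** 1. In protocol 11.3.7 and SAP 5.6.2, define a TEAE as an event that starts, or worsens in intensity or seriousness, after the first administration.
2. In protocol 9.1.3 and the CRF completion instructions, require a post-dose worsening to be entered as a new AE with its own onset date and time, while the existing record keeps its earlier intensity. Without a recorded time of worsening, the new definition cannot be programmed.
3. In protocol 11.3.7 and SAP 5.6.2, allocate the new AE to the last product given before the worsening.

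The cost is about one sentence in each document and in the CRF instructions. The downside is a slightly higher AE count. No planned analysis is lost.

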11.3.8 Laboratory biological data

Laboratory data analysis will be done using the safety set.

The baseline is defined as the last measure before the first trial product administration.

The statistical analysis will present results (see section 7.2) in standard international units and conventional United States units. Original units will be only listed. Laboratory data will be analyzed quantitatively and qualitatively. Qualitative analyses will be done via comparison of laboratory data to their reference ranges and according to their clinical significance. Quantitative analyses will be done by tabulating raw data and change from baseline. They will be displayed qualitatively as well by means of shift tables.

11.3.9 Other safety observations

Other safety observation will be presented on the safety set.

Extent of exposure

Duration between IMP/AMP administrations and end of trial, volume/dose theoretically administered, volume/dose actually administered, actual IMP rate of administration, theoretical IMP rate of administration and location of injection site will be tabulated. Frequency tabulation of theoretical volume/dose actually administered and theoretical rate of administration/dose actually performed will be also displayed per trial products groups and overall.

Vital signs

The baseline is defined as the last measure before the first trial product administration.

Vital signs (see section 7.2) will be analyzed quantitatively and qualitatively. Qualitative analyses will be done via comparison of vital signs data to their normal ranges and according to their clinical significant changes. Quantitative analyses will be done by tabulating raw data and change from baseline.

ECG data

The baseline is defined as the last measure before each IMP/AMP administration.

ECG data (see section 7.2) will be analyzed quantitatively and qualitatively. Qualitative analyses will be done via comparison of ECG data to their normal ranges and according to their clinical significant changes. Quantitative analyses will be done by tabulating raw data and change from baseline.

Injection site tolerance

Number of subjects experiencing burning, pain, eruption, extravasation and inflammation at site injection will be tabulated per IMPs groups and overall. Pain at injection site will be measured using the Visual Assessment Scale (VAS) and VAS measurements for these subjects will be tabulated.

11.4 Statistical/Analytical issues

11.4.1 Adjustment for covariates

For the primary analysis and the assay sensitivity, covariates (baseline of the primary endpoint and sex) are taken into account in the models used for the analyses.

11.4.2 Handling of Dropouts or Missing Data

No imputation will be performed in this trial.

11.4.3 Interim Analysis

Not applicable

11.4.4 Multicentre Trials

Not applicable

11.4.5 Multiple Comparisons/Multiplicity

As stated in [sections 11.1 and 11.3.6](#), the multiplicity is handled by considering a study “negative” (that is to say successful) if both P03277 doses rejects simultaneously the null hypothesis for all timepoints **and** if for the assay sensitivity, the null hypothesis is rejected at, at least, one timepoint, using the method described by Hochberg and Tamhane to deal with multiple timepoints.

11.4.6 Use of a subset of Subjects for Cardiac Safety Analysis

Because the primary analysis is a non-inferiority analysis, it will be done using the Per Protocol Set and then the analysis will be repeated using the Full Analysis Set. The assay sensitivity analysis will be done using the Full Analysis Set and then repeated using the Per Protocol Set

11.4.7 Active control trials Intended to Show Equivalence

Not applicable

11.4.8 Examination of Subgroups

The trial is stratified by sex which will be taken into account for the primary analysis and the assay sensitivity by putting it in the model. No other examination of subgroups is planned.

12 TRIAL COMMITTEE

The purpose of this phase I trial as per current ICH E14 Guidance, is to satisfy with the regulatory requirement for a new drug in development to conduct a thorough QT/QTc trial in order to demonstrate that P03277 does not prolong the QT and QTc intervals in healthy volunteers.

P03277 is a MRI contrast agent belonging to a well-known product class (GBCA) and there is, a priori, no particular expected safety concerns. In addition, the P03277 has a linear pharmacokinetic profile similar to the other Gd chelates and the preliminary results obtained during the phase I trial with several doses of P03277 showed no clinical and biological alert signal.

Regarding placebo there is no particular expected safety concerns. The positive control is a well-known fluoroquinolone which has been shown to prolong the QTc interval on the electrocardiogram in some patients.

The trial duration per subject is maximum 122 days, P03277 are injected at two different doses in addition of Placebo and Positive Control. The P03277 doses selected for the current trial have been tested as single dose during the phase I trial for which no safety alert was identified.

Trial stopping rules and specific subjects stopping rules have been set up in the trial protocol ([see section 10.2](#)) and check points at patient level are done before to proceed to any injection (in order to keep the blind conditions).

For all these reasons, an IDMC (Independent Data Monitoring Committee) has not been established for the trial.

However, a Data Monitoring Committee (DMC) will be set up for assessing the safety of P03277 during the trial and for monitoring the overall conduct of the clinical trial as well as ensuring that the trial and subjects stopping rules for safety reasons are applied when required.

The DMC members will be: the principal investigator and Guerbet team (drug safety physician, Medical Expert, clinical project manager and ad-hoc team members). All the members will remain blinded regarding all the trial data. The role and responsibilities of this DMC will be described in a separate document (Data Safety Monitoring Plan).

- Commission Directive 2005/28/EC of 8 April 2005 laying down principles and detailed guidelines for good clinical practice as regards investigational medicinal products for human use, as well as the requirements for authorisation of the manufacturing or importation of such products
- International Conference on Harmonisation (ICH) of Technical Requirements for Registration of Pharmaceuticals for Human Use: Ethnic Factors in the Acceptability of Foreign Clinical Data E5(R1) Current Step 4 version dated 5 February 1998
- EudraLex, The Rules Governing Medicinal Products in the European Union, Volume 4, EU Guidelines to Good Manufacturing Practice - Medicinal Products for Human and Veterinary Use, Annex 13 Investigational Medicinal Products
- US Food and Drug Administration, Title 21 Code of Federal Regulations Part 11 on Electronic Records; Electronic Signatures

 CONFIDENTIAL	Protocol No. GDX-44-006 Version No. 5.0 including amendment 03 Date 31 August 2018	Page 72 / 80
---------------------------------------------------------------------------------------------------	------------------------------------------------------------------------------------------	--------------

- US Food and Drug Administration, Title 21 Code of Federal Regulations Part 211 on Current Good Manufacturing Practice for Finished Pharmaceuticals
- US Food and Drug Administration, Title 21 Code of Federal Regulations Part 54 Financial Disclosure By Clinical Investigators
- Regional / local regulations and other specific populations regulations

13.2 Institutional Review Board/Independent Ethics Committee and Regulatory/Competent Authorities

As per international regulation, the clinical trial may be initiated only after having received the approval by and Institutional Review Board/Independent Ethics Committee (IRB/IEC) and the authorization by the national Regulatory/Competent Authority. The final written approval and authorization must be available for a given investigational site when initiating the trial conduct at this particular site. Amongst all documents required locally, the approval and authorization must be obtained for the protocol, investigator's brochure/SmPC, the subject informed consent form and any other written information or document to be provided to the subjects.

In case of modifications to the trial protocol, subject informed consent form or any other written information provided to the subjects, or to any trial procedure; the modified documents will be submitted to IRB/IEC and Regulatory/Competent Authority opinions. Modifications may be implemented when the final approval and authorization are available.

In case of an emergency situation when the subjects' safety may be at risk, Guerbet may implement emergency safety measures prior to obtaining IRB/IEC approval and Regulatory/Competent Authority opinion. In parallel to implementing these measures, Guerbet will immediately notify the concerned IRB/IEC and Regulatory/Competent Authorities of such implementation.

The documentation related to the approvals and authorizations must be filed in the Trial Master File at Guerbet and at the investigational sites in their respective Investigational Site File (ISF)

Notifications of Serious Adverse Events/Reactions to IRB/IEC and Regulatory/Competent Authority will be made according to the national requirements. Safety reporting is described in [section 9](#) of the present protocol.

Notifications of non-compliances / deviations to IRB/IEC and Regulatory/Competent Authority will be made according to national requirements of participating countries and according to individual IRB/IEC requirements when applicable

